#### 10.5.2.3 Data handling principles

Plasma concentration values below the lower limit of quantification (LLOQ) will be set to zero by the bioanalyst, and will be displayed as zero in the listings and flagged. Values below the LLOQ will be treated as zero in any calculations of summary statistics, and treated as missing for the calculation of the geometric means and their CV%. Any missing pharmacokinetic parameters or concentrations will not be imputed.

10.5.4 Resource utilization

Not applicable.

#### 10.5.5 Patient-reported outcomes

Patient reported outcome (PRO) will only be evaluated in the LGG cohort. One PRO questionnaire will be used: the PROMIS Parent Proxy Global Health 7+2. The 7+2 item parent proxy pediatric global health measure include a one global health score plus a single score from pain and a score from fatigue interference item which are scored independently. These two items are administered but do not contribute to the global health score. Rather, they are "signal" items that provide initial score estimates for pain interference and fatigue. Scoring of PRO data and methods for handling of missing items or missing assessments will be according to the scoring manual and user guide for each respective patient questionnaire. No imputation procedures will be applied for missing items or missing assessments. Descriptive statistics will be used to summarize the scored scales of PROMIS Parent Proxy Global Health 7+2 at each scheduled assessment time point for each treatment group. Additionally, change from baseline in the scale at the time of each assessment will be summarized. Subjects with an evaluable baseline score and at least one evaluable post baseline score during the treatment period will be included in the change from baseline analyses. In addition, a repeated measures model for longitudinal data will be used to estimate differences in PROMIS Parent Proxy Global Health 7+2 scores between treatment groups. The number of subjects completing each questionnaire and the number of missing or incomplete assessments will be summarized by treatment group for each scheduled assessment time point. No formal statistical tests will be performed for PRO data and hence no multiplicity adjustment will be applied. The FAS will be used for analyzing PRO data.

#### 10.7 Interim analysis

#### 10.7.1 HGG Cohort

An interim analysis for futility (HGG cohort only) will be implemented to allow possible termination of recruitment and the study in the event that there is insufficient efficacy. The patients for inclusion in the formal interim analysis for futility will be made shortly after 16 patients in the FAS have been enrolled. The interim analysis will be conducted when this initial group of patients to be included in the analysis have all had at least 20 weeks of follow-up or have withdrawn early. However, any decision to stop or continue the study will be made based on all data available at the IA cut-off taking the futility analysis into account.

The futility criteria will be considered met if the observed overall response rate (ORR) assessed by independent reviewer is less than or equal to 25% which is considered a threshold for clinical relevance. This will trigger consideration for stopping the study taking account of all available data and not just the response data required for determination of futility.

The choice of futility threshold has also taken account of operating characteristics which suggest that the chance of the futility criteria being met is high if the true underlying response rate is in a low range (e.g. <=20%); whereas if the true rate is considerably higher, as expected, then there is a very low chance of declaring futility at the IA. Full details of the futility criteria and operating characteristics are provided below in Table 10-2 and Table 10-4.

#### **Futility criteria**

Given the data observed in the IA, the probability of the lower bound of 95% CI at the primary analysis exceeding a certain response rate (i.e. 20%) conditional on the observed number of responders observed at the IA can be calculated. The conditional probability can be calculated using beta-binomial distribution (posterior predictive distribution). Let Y represent the number of responders from m future patients at the primary analysis and x is the number of responders among n patients at the interim analysis. The (posterior) predictive distribution of Y conditioned on the observed data at the interim analysis (x responders out of n patients) is a beta-binomial distribution described by

$$p(Y = y | x, n) = {m \choose y} \frac{B(a_0 + x + y, b_0 + n - x + m - y)}{B(a_0 + x, b_0 + n - x)}$$

where a minimally informative unimodal Beta distribution B(a0, b0) (Neuenschwander et al 2008) is used with mean equal to 20%, i.e., the prior distribution will be Beta (0.25, 1) for the POS calculations at the interim analysis.

Table 10-2 shows the predictive probabilities that the 95% CI excludes 20% at the primary analysis under different interim results. For example, with 16 patients at IA, if 4 responses are observed (i.e. 25% response rate), the probability of the 95% CI excluding 20% at the primary analysis is 13.7%.

Table 10-2 Predictive probability of the lower bound of 95% CI exceeding 20% at the primary analysis under different interim results

| # of responses | Observed response rate at IA given n=16 (%) | Predictive probability that the 95% CI excludes 20% at the primary analysis (%) a |
|----------------|---|--|
| 1              | 6.3   | < 0.1  |
| 2              | 12.5  | 0.5  |
| 3              | 18.8  | 3.5  |
| 4              | 25.0  | 13.7   |
| 5              | 31.3  | 34.4   |
| 6              | 37.5  | 61.0   |
| 7              | 43.8  | 83.1   |
| 8              | 50.0  | 94.9   |
| 9              | 56.3  | 99.0   |

<sup>aThe predictive probabilities are calculated from a beta-binomial distribution.

In addition to the interim futility analysis described above if the LGG primary analysis is subsequently reported prior to the HGG primary analysis then an update/interim analysis of HGG safety data only may be required to support the LGG submission.

Also, an additional interim analysis of key safety and PK data of the adolescent patients in the HGG cohort may be performed to support a heath authority request for data in adolescent patients. There will be no efficacy or futility conclusion drawn based on this interim analysis.

#### 10.7.2 **LGG Cohort**

No formal interim analysis is planned for the LGG cohort. The primary analysis will be performed after all patients have completed Week 32 or discontinued prior to Week 32. A final analysis will be performed after all patients have been on the study for at least two years (or otherwise discontinued from the study). Formal testing of the primary endpoint with full alpha will be performed at the primary analysis.

#### 10.8 Sample size calculation

#### 10.8.1 **HGG Cohort**

Based on the exact binomial distribution, approximately 40 patients will be enrolled if the study is not stopped for futility at the time of the interim analysis.

The exact 95% and 80% CIs for potential observed ORR for 40 patients are shown in Table 10-3.

The 95% CI, via the lower limit, is used to establish the levels of response which are exceeded by taking the combination therapy according to a robust standard of evidence (i.e. one-sided alpha=0.025).

Due to the uncertainties regarding the historical control data there is no specific "success" threshold level that we can apply that the lower limit should be greater than to give robust evidence that dabrafenib and trametinib combination therapy is better than historical control; however, the study sample size gives reasonable operating characteristics for an illustrative threshold historical level of 20%, which is higher than the range expected based on the information given in the literature (Section 1.1.3).

The study also aims to provide evidence that trametinib gives added value to the dabrafenib and trametinib combination over and above dabrafenib monotherapy treatment. Since a lower standard of evidence is usually required to show such added value, the lower limit of an 80% CI is used to identify the response rates which will be exceeded by taking the combination therapy based on a reduced level of evidence (one-sided alpha of 0.1). Again it is difficult to ascertain a definitive threshold for "success" for evaluation in these circumstances but the number of patients in this trial give reasonable operating characteristics for an illustrative threshold level of 32%, which is the response rate observed in dabrafenib monotherapy patients in the study [BRF116013, CDRB436A2102] although based on limited data. Note that the 95% CIs can also be used to provide more robust evidence of the benefit of trametinib by looking at the lower limit compared to possible levels of dabrafenib monotherapy response.

Table 10-3 Exact Binomial 95 and 80 percent Confidence Intervals Around Potential Observed ORRs for N=40

| Number of responders | Observed ORR (%) | 95% exact CI (%) | 80% exact CI (%) |
|----------------------|------------------|------------------|------------------|
| 12                   | 30.0             | 16.6, 46.5       | 20.5, 41.2       |
| 13                   | 32.5             | 18.6, 49.1       | 22.7, 43.8       |
| 14                   | 35.0             | 20.6, 51.7       | 24.9, 46.3       |
| 15                   | 37.5             | 22.7, 54.2       | 27.1, 48.9       |
| 16                   | 40.0             | 24.9, 56.7       | 29.4, 51.4       |
| 17                   | 42.5             | 27.0, 59.1       | 31.7, 53.9       |
| 18                   | 45.0             | 29.3, 61.5       | 34.1, 56.3       |
| 19                   | 47.5             | 31.5, 63.9       | 36.4, 58.8       |
| 20                   | 50.0             | 33.8, 66.2       | 38.8, 61.2       |
| 21                   | 52.5             | 36.1, 68.5       | 41.2, 63.6       |
| 22                   | 55.0             | 38.5, 70.7       | 43.7, 65.9       |

For example, out of the 40 patients, with 14 responses (35%), the lower bound of 95% CI would be higher than 20%; with 18 responses (45%), the 80% CI would be higher than 32%; and with 20 responses (50%), the 95% CI would be higher than 32%.

Table 10-4 and Table 10-5 show the operating characteristics under different true ORR with respect to different criteria. The tables show probability of meeting the futility consideration criteria (less than 5 responders out of 16 patients), probability of the confidence interval excluding the target response rate at the primary analysis, and probability that the futility criteria is not met at IA but the confidence interval does not exclude the target response rate at the primary analysis.

At this sample size, when the true ORR is  $\leq 20\%$ ,

- the probability of meeting the futility consideration criteria at interim analysis is > 79%,
- the probability of the 95% CI excluding 20% at the primary analysis is >1.6%,
- and the probabilities of the 95% CI and the 80% CI excluding 32% at the primary analysis are both < 0.1% respectively.

Within 40 patients, if the true ORR is 55% or higher, then

- the probability of meeting the futility consideration criteria at IA is < 2%,
- the probabilities of the 95% CI excluding 20% and the 80% CI excluding 32% at the primary analysis are both > 90% respectively,
- and the probability that the 95% CI excludes 32% is > 78%.

Table 10-4 Operating Characteristics with regard to the 95% CI excluding 20% response rate

| True
ORR (%) | Probability to
meet futility
consideration
criteria at IA (%) | Probability that the futility consideration criteria is not met at IA and the 95% CI excludes 20% at primary analysis (%) | Probability that the futility consideration criteria is not met at IA and the 95% CI does not exclude 20% at primary analysis (%) |
|-----------------|--|---|---|
| 20              | 79.8   | 1.6   | 18.6  |
| 25              | 63.0   | 8.5   | 28.4  |
| 30              | 45.0   | 25.2  | 29.8  |
| 35              | 28.9   | 49.1  | 22.0  |

| True
ORR (%) | Probability to
meet futility
consideration
criteria at IA (%) | Probability that the futility consideration criteria is not met at IA and the 95% CI excludes 20% at primary analysis (%) | Probability that the futility consideration criteria is not met at IA and the 95% CI does not exclude 20% at primary analysis (%) |
|-----------------|--|---|---|
| 40              | 16.7   | 71.7  | 11.6  |
| 45              | 8.5  | 87.1  | 4.4   |
| 50              | 3.8  | 95.0  | 1.2   |
| 55              | 1.5  | 98.3  | 0.2   |
| 60              | 0.5  | 99.5  | < 0.1   |

The probabilities are calculated based on the exact binomial distribution.

Table 10-5 Operating Characteristics with regard to the 95% and 80% Cls excluding 32% response rate

| True ORR
(%) | Probability to
meet futility
consideration
criteria at IA
(%) | Probability that
the futility
consideration
criteria is not
met at IA and
the 95% CI
excludes 32%
at primary
analysis (%) | Probability that the futility consideration criteria is not met at IA and the 95% CI does not exclude 32% at primary analysis (%) | Probability that
the futility
consideration
criteria is not
met at IA and
the 80% CI
excludes 32%
at primary
analysis (%) | Probability that the futility consideration criteria is not met at IA and the 80% CI does not exclude 32% at primary analysis (%) |
|-----------------|---|---|---|---|---|
| 20              | 79.8  | < 0.1   | 20.2  | < 0.1   | 20.1  |
| 25              | 63.0  | 0.1   | 36.9  | 0.5   | 36.5  |
| 30              | 45.0  | 0.6   | 54.4  | 3.1   | 51.9  |
| 35              | 28.9  | 3.6   | 67.5  | 12.1  | 59.0  |
| 40              | 16.7  | 12.9  | 70.5  | 30.5  | 52.9  |
| 45              | 8.5   | 31.4  | 60.1  | 55.2  | 36.3  |
| 50              | 3.8   | 56.0  | 40.1  | 77.6  | 18.5  |
| 55              | 1.5   | 78.5  | 20.0  | 91.7  | 6.8   |
| 60              | 0.5   | 92.4  | 7.1   | 97.8  | 1.7   |

The probabilities are calculated based on the exact binomial distribution.

#### 10.8.2 LGG Cohort

To detect a 30% improvement in ORR based on central independent assessed response of 50% in the dabrafenib plus trametinib arm vs 20% in the carboplatin with vincristine arm (Lassaletta 2017) with at least 80% power, 102 patients are required to be randomized in the two treatment arms in a 2:1 ratio based on using a\_Maentel-Haenszel chi-squared test and one-sided alpha = 2.5%.

Based on the following assumptions i.e 102 patients, 2:1 randomization ratio based on Maentel-Haenszel chi-squared test and one sided alpha of 2.5%, the study power scenarios under different true ORR are shown in Table 10-6.

| Protocol | Amenaea | version | U5 |
|----------|---------|---------|----|
|          |         |         |    |

Table 10-6 Power scenarios under different true ORR in BRAF V600 mutant

| LGGTrue ORR % (carboplatin with vincristine arm vs. dabrafenib plus trametinib) | Power (%) |
|---|-----------|
| 20% vs. 55%   | 90%       |
| 20% vs. 50%   | 80%       |
| 20% vs. 45%   | 67%       |
| 15% vs. 50%   | 90%       |
| 25% vs. 50%   | 66%       |

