#### Sample size for HGG cohort:

Approximately 40 patients will be enrolled in HGG cohort if the study is not stopped for futility at the time of IA.

|           | With a total of 40 patients and with 16 patients included in the futility interim analysis and when the true ORR is ≤ 20%:   |
|-----------|--|
|           | 
 
the probability of meeting the futility consideration criteria at IA is > 79%,
 
  |
|           | • the probability of the 95% CI excluding 20% at the primary analysis is < 1.6%,   |
|           | 
 
and the probabilities of the 95% CI and the 80% CI excluding 32% at the
primary analysis are both < 0.1% respectively.
 
  |
|           | With a total of 40 patients and with 16 patients included in the futility interim analysis and if the true ORR is 55% or higher, then:   |
|           | 
 
the probability of meeting the futility consideration criteria at IA is < 2%,
 
   |
|           | 
 
the probabilities of the 95% CI excluding 20% and the 80% CI excluding 32%
at the primary analysis are both > 90% respectively,
 
   |
|           | 
 
and the probability that the 95% CI excludes 32% is > 78%.
 
  |
|           | Sample size for LGG cohort:  |
|           | For LGG cohort, to detect a 30% improvement in ORR based on central independent assessment response of 50% in the dabrafenib in combination with trametinib arm vs 20% in the carboplatin plus vincristine arm with at least 80% power, 102 patients are required to be randomized in the two treatment arms in a 2:1 ratio using a Maentel-Haenszel chi-squared test, and one-sided alpha = 2.5%. |
| Key words | High grade glioma, HGG, Low grade glioma, LGG, BRAF , DRB436, dabrafenib, TMT212, trametinib, carboplatin and vincristine, children, adolescent   |

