#### **LGG Cohort**

The primary efficacy analysis in the LGG cohort is the comparison of ORR based on independent review assessment between the two treatment arms. The following statistical hypothesis will be tested:

$$H_{01}$$
:  $ORR_t \leq ORR_c$  vs.  $H_{A1}$ :  $ORR_t > ORR_c$ 

where  $ORR_t$  is the ORR in the Trametinib plus Dabrafenib arm and  $ORR_c$  is the ORR in the carboplatin with vincristine arm. The analysis to test these hypotheses and compare the two treatment groups will consist of a Mantel Haenszel chi-square test at one-sided 2.5% level of significance.

The primary efficacy analysis will be performed on the FAS.

ORR will be summarized using descriptive statistics (N, %) by treatment arm along with two-sided exact binomial 95% CIs (Clopper and Pearson 1934).

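### The HGG false-positive rate is printed as both below and above 1.6%, and both statements omit the condition under which 1.6% was calculated (1.94% without it)

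*Protocol*

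**What the plan says.** **HGG.** The protocol summary (sample size for the HGG cohort) and Section 10.8.1 each list operating characteristics for a true response rate of 20% or less. The summary says "the probability of the 95% CI excluding 20% at the primary analysis is < 1.6" per cent. Section 10.8.1 says "the probability of the 95% CI excluding 20% at the primary analysis is >1.6" per cent. Table 10-4, which follows in Section 10.8.1, prints 1.6 in the row for a true rate of 20%. Its column heading describes a joint event: the futility criterion is not met at the interim, and the 95% interval excludes 20% at the primary analysis.

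Sections 4.2 and 10.7.1 make the futility rule advisory. An observed rate of 25% or less among the 16 interim patients leads to consideration of stopping, and the decision takes account of all data available at the interim cut-off.

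**LGG.** Section 10.8.2 assumes "50% in the dabrafenib plus trametinib arm vs 20% in the carboplatin with vincristine arm" and concludes that "with at least 80% power, 102 patients are required to be randomized in the two treatment arms in a 2:1 ratio". It then states that "the study power scenarios under different true ORR are shown in Table 10-6", on the basis of the "Maentel-Haenszel chi-squared test and one sided alpha of 2.5" per cent. Section 10.4.2 names the same analysis: a "Mantel Haenszel chi-square test at one-sided 2.5% level of significance". Table 10-6 gives 90, 80, 67, 90 and 66% for 20 vs 55, 20 vs 50, 20 vs 45, 15 vs 50 and 25 vs 50.

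**The concern.** For the HGG cohort, the chance of a favourable result when the true rate is no better than 20% is a main safeguard of a single-arm design. Printed once as an upper limit and once as a lower limit, it tells the reader nothing definite. The version in Section 10.8.1 puts no ceiling on the error at all.

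The second difficulty remains once the sign is corrected. Both bullets present 1.6% as the plain probability that the interval excludes 20%. It has that value only if every crossing of the futility line ends enrolment, and the protocol does not commit to that. A reader who relies on the bullet takes a conditional figure for an unconditional one.

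For the LGG cohort, a reader who checks the printed powers against the named chi-square gets different numbers and may doubt the sample size.

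**Working it through.** **HGG inputs.** Success is at least 14 responders of 40: Table 10-3 gives a lower 95% limit of 20.6% for 14 and 18.6% for 13. Futility is 4 or fewer of 16 (Sections 10.7.1 and 10.8.1). That leaves 40 − 16 = 24 patients after the interim. The true rate is 20%.

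**Step 1: reproduce Table 10-4.** With X ~ Bin(16, 0.20) and Y ~ Bin(24, 0.20):

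- Futility met: P(X ≤ 4) = 79.8%.
- Futility not met and success: sum over k = 5 to 16 of P(X = k) × P(Y ≥ 14 − k) = 1.57%.
- Futility not met and no success: 100 − 79.8 − 1.6 = 18.6%.

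The table prints 79.8, 1.6 and 18.6, so it is correct for the event in its heading.

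**Step 2: direction of the inequality.** At a true rate of 15% the same joint probability is 0.11%. It falls as the true rate falls, so over all rates up to 20% it is at most 1.57%. For the tabulated event the summary has the right direction and Section 10.8.1 has the sign reversed.

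**Step 3: the event that the bullets describe.** Without the futility condition, P(Bin(40, 0.20) ≥ 14) = 1.94%. The difference comes from patients' results that cross the futility line and still reach 14:

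| Responders of 16 | P(X = k) | P(Y ≥ 14 − k) | Product |
|---|---|---|---|
| 4 | 0.2001 | 0.01262 | 0.00253 |
| 3 | 0.2463 | 0.00379 | 0.00093 |
| 2 | 0.2111 | 0.00098 | 0.00021 |
| 0 or 1 | | | 0.00003 |

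The products sum to 0.0037, and 1.57% + 0.37% = 1.94%. At a true rate of 15% the unconditional figure is 0.14%.

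**Step 4: do the other bullets depend on the condition?** No. The figures below are with the condition, then without it.

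- True rate 20%, 80% and 95% intervals excluding 32%: 0.029% vs 0.030% and 0.002% vs 0.002%, all below 0.1%.
- True rate 55%, 95% interval excluding 20%: 98.3% vs 99.7%.
- True rate 55%, 80% interval excluding 32%: 91.7% vs 92.3%.
- True rate 55%, 95% interval excluding 32%: 78.5% vs 78.7%.

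Each of those statements holds either way. Only the 1.6% bullet changes.

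**LGG inputs.** 34 control and 68 experimental patients, one-sided 2.5% (z = 1.96), rates as in Table 10-6.

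**Step 5: reproduce Table 10-6.** On the log-odds-ratio scale, power = Φ(L/SE − 1.96), with L = ln[p_t(1 − p_c) / (p_c(1 − p_t))] and SE² = 1/(34 p_c q_c) + 1/(68 p_t q_t), where q = 1 − p. For 20 vs 50: L = ln 4 = 1.386; SE² = 1/5.44 + 1/17 = 0.2427; SE = 0.4926; L/SE = 2.814; power = Φ(0.854) = 80.4%.

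| Control vs experimental | Table 10-6 | Log-odds-ratio formula | Exact, Mantel-Haenszel chi-square | Exact minus stated |
|---|---|---|---|---|
| 20 vs 55 | 90 | 89.6 | 94.3 | 4.3 |
| 20 vs 50 | 80 | 80.4 | 86.3 | 6.3 |
| 20 vs 45 | 67 | 67.1 | 72.5 | 5.5 |
| 15 vs 50 | 90 | 89.7 | 95.9 | 5.9 |
| 25 vs 50 | 66 | 65.7 | 69.6 | 3.6 |

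All five rows match after rounding. With 33:66 the formula gives 79.2%, so 102 is the smallest 2:1 total that reaches 80% under it.

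**Step 6: the named test.** The exact column sums the product of the two binomial probabilities over all outcomes for which the uncorrected Mantel-Haenszel statistic is at least 1.96. By that calculation 87 patients (29:58) already give 80.4% for 20 vs 50. The pooled normal approximation reaches 80.9% at 90.

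**The case against.** The case for leaving the text alone has weight. Table 10-4 labels its event correctly and follows shortly after the faulty bullet, the summary has the right direction, and the advisory nature of the futility rule is stated openly in several sections. The gap between 1.57% and 1.94% lies wholly below the 2.5% of Section 10.4.2. Section 10.8.1 also calls the 20% threshold illustrative and sets no formal success level, so no decision turns on this figure. All of that stands, and it limits the point to a correction of text. It does not remove the contradiction between the two bullets. Nor does it make the summary's limit true for the unconditional event that the bullet describes, since 1.94% exceeds 1.6%.

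On the LGG side, a reader who tries the chi-square, a continuity correction or Fisher's test might infer that Table 10-6 cannot be reproduced from any standard method, or that some rows are too high. The documents do not support either reading. A standard large-sample formula reproduces every row and N. Rows look too high only under a corrected or exact test, which the protocol does not name. Against the test it does name, every printed figure is on the low side, so the claim of at least 80% power is true. A conservative planning formula is a legitimate choice.

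**Conclusion.** The HGG point holds. Two statements of the same probability contradict each other, and neither carries the condition on which the number depends. At a true rate of 20% the correct figures are 1.57% if crossing the futility line always ends enrolment and 1.94% if it never does; partial adherence falls between them. A reader might infer from the reversed sign that the false-positive rate is uncontrolled. It is not: both figures are below 2.5%. They assume exactly 16 and 40 patients and independent responses with a common rate. Enrolment is described as approximate, so the values would shift a little with other totals.

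The LGG point is a clarification only. The approximation behind Table 10-6 is not named and is 3.6 to 6.3 percentage points below the exact power of the named test. The word *required* is right under that approximation and stronger than the named test needs. The sample size is adequate either way.

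**What to change.** 1. In the protocol summary and in Section 10.8.1, replace the bullet by one statement: for true rates up to 20%, the probability that the 95% interval excludes 20% is at most 1.6% if the futility criterion is followed and at most 1.9% if it is not (1.57% and 1.94% before rounding), both below 2.5%.
2. In Section 10.8.2, name the log-odds-ratio normal approximation at 68:34 as the source of N and Table 10-6. Alternatively, add that 102 patients give about 86% power for 50% vs 20% with the Mantel-Haenszel chi-square.

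The cost is a few words in three places. Sample sizes, alpha, tests, the futility threshold and the conduct of the trial do not change, and Tables 10-4 and 10-6 can stay as printed.
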